13.3. Case Report Forms / Electronic Data Record

As used in this protocol, the term case report form (CRF) should be understood to refer to either a paper form or an electronic data record or both, depending on the data collection method used in this study.

Investigational Device: ThermiRF

Protocol No.: Thermi_0005

Version Date: Final 10-May-2016

A CRF is required and should be completed for each enrolled subject. The completed original CRFs are the sole property of the sponsor and should not be made available in any form to third parties, except for authorized representatives of the sponsor or appropriate regulatory authorities, without written permission from the sponsor.

It is the investigator's responsibility to ensure completion, review and approve all CRFs. CRFs must be signed by the investigator or by an authorized staff member. These signatures serve to attest that the information contained on the CRFs is true and accurate.

At all times, the investigator has final personal responsibility for the accuracy and authenticity of all clinical and laboratory data entered on the CRFs. In cases where the source documents are the hospital or the physician's chart, the information collected on the CRFs must match those charts.

13.4. Record Retention

To enable evaluations and/or audits from regulatory authorities or the Sponsor, the investigator agrees to keep records including the identity of all participating subjects (sufficient information to link records, e.g., CRFs and hospital records), all original signed informed consent forms, copies of all CRFs, serious adverse event forms, source documents, and detailed records of treatment disposition. The records should be retained by the investigator according to ICH guidelines, local regulations, or as specified in the Clinical Study Agreement, whichever is longer.

If the investigator relocates, retires, or for any reason withdraws from the study, the Sponsor should be prospectively notified of the event, and the location of study records.

The study records must be transferred to an acceptable designee, such as another investigator, another institution, or to the Sponsor.

The investigator must obtain Sponsor's written permission before disposing of any records, even if retention requirements have been met.

Investigational Device: ThermiRF

Protocol No.: Thermi_0005

Version Date: Final 10-May-2016

14. SPONSOR DISCONTINUATION CRITERIA

Premature termination of this clinical study may occur because of a regulatory authority decision, change in opinion of the IRB/IEC, device safety problems, or at the discretion of the sponsor. In addition, the sponsor retains the right to discontinue development of the device at any time.

If a study is prematurely terminated or discontinued, the sponsor will promptly notify the investigator. After notification, the investigator must contact all participating subjects within 2 weeks from study termination. All study materials must be collected and all CRFs completed to the greatest extent possible.

Investigational Device: ThermiRF

Protocol No.: Thermi_0005

Version Date: Final 10-May-2016

15. PUBLICATION OF STUDY RESULTS

Publication of study results by the investigator is discussed in the Clinical Study Agreement, as appropriate. Results from this study may be published in the form of oral or written presentations at scientific meetings or as one or more peer-reviewed journal articles. In these cases, no information on individual subjects will be revealed.

Investigational Device: ThermiRF

Protocol No.: Thermi_0005

Version Date: Final 10-May-2016

APPENDIX 1 SCHEDE OF EVALUATIONS

	Visit 1 Screening	Visit 2 (Treatment) (n=70)	Visit 3 Day 30	Visit 4 (F/U) Day 60 (n=first 30)	Visit 5 (F/U) Day 90	Visit 6 (F/U) Day 180 (EOS)
Informed consent	X					
Medical /Medication History	X					
Demographics and Baseline Characteristics	X					
Inclusion/Exclusion criteria/conformance	X	X ¹				
Urine Pregnancy Test		X ¹				
Brief Physical Evaluation and Medical Clearance	X					
Vital Signs (incl. Height & Weight)	X					
Photography – 2D (Left, Right and Front views)	X ²			X ²	X ²	X ²
Photography 3D	X ³			X ³	X ³	X ³
Elasticity measurement	X				X	X
Treatment Administration		X				
NRS pain scale			X		X	X
S-GAIS, S-GSQ				X	X	X
P-GAIS, P-GSQ					X	X
Concomitant Medications		X	X		X	X
Adverse events		X	X		X	X

¹ Urine pregnancy test must be conducted prior to treatment

² All 2D images must be collected using standard camera and lighting. Positioning of images must be *Front View, Right and Left Lateral view and Right and Left views at a 45° angle*.

³ All 3D images must be collected using the Vectra XT camera.

⁴ Visit 4 only applies to the first 30 subjects enrolled in the study.

Investigational Device: ThermoRF

Protocol No.: Thermo_0005

Version Date: Final 10-May-2016

APPENDIX 2 PHYSICIAN GLOBAL AESTHETIC IMPROVEMENT SCALE (P-GAIS)

PHYSICIAN GLOBAL AESTHETIC IMPROVEMENT SCALE (P-GAIS)		
Compared to baseline photography, how would you rate the appearance of the subjects neck laxity with respect to " lift "	5.  Very Much Improved	Optimal cosmetic result for this volunteer.
	4.  Much Improved	Marked improvement in appearance from the initial condition, but not completely optimal for this volunteer. A touch-up would slightly improve the result.
	3.  Improved	Obvious improvement in appearance from the initial condition, but a touch-up or retreatment is indicated
	2.  No Change	The appearance is essentially the same as the original condition
	1.  Worse	The appearance is worse than the original condition

Investigational Device: ThermoRF

Protocol No.: Thermo_0005

Version Date: Final 10-May-2016

APPENDIX 3 SUBJECT- GLOBAL AESTHETIC IMPROVEMENT SCALE (S-GAIS)

SUBJECT GLOBAL AESTHETIC IMPROVEMENT SCALE (S-GAIS)		
Compared to baseline how would you rate the appearance of your neck with respect to "lift"	5.  Very Much Improved	Optimal cosmetic result for this volunteer.
	4.  Much Improved	Marked improvement in appearance from the initial condition, but not completely optimal for this volunteer. A touch-up would slightly improve the result.
	3.  Improved	Obvious improvement in appearance from the initial condition, but a touch-up or retreatment is indicated
	2.  No Change	The appearance is essentially the same as the original condition
	1.  Worse	The appearance is worse than the original condition

Investigational Device: ThermoRF

Protocol No.: Thermo_0005

Version Date: Final 10-May-2016

APPENDIX 4 PHYSICIAN- GLOBAL SATISFACTION QUESTIONNAIRE (P-GSQ) OF THE NECK

STUDY NO.: THERMI_005	VISIT DAE: VISIT DAY:  90  180
PHYSICIAN GLOBAL SATISFACTION QUESTIONNAIRE (P-GSQ) OF THE NECK	
1. When looking at the photo images and respective to your clinician assessment during this visit, do you see any change on the treated area with respect to "improvement" of the skin and overall area?	 Yes, if "yes" please check all that apply:  Less sagging on the jawline and cheeks  Tighter/lift under the chin area  Smoother skin texture  Jaw line more defined  less wrinkles/lines  Other (specify); _____  No
2. Compared to "BEFORE" treatment how does the subject's skin feel today (check all that apply)?	 Tighter  Firmer  Smoother  Make-up application easier  Shaving easier  No change from prior to treatment
3. How satisfied are you with the results of the treatment.	 Very Satisfied  Satisfied  Neutral  Dissatisfied  Very dissatisfied
4. How likely are you to recommend the treatment to your patients?	 Very likely  Likely  Neutral  Unlikely  Vert unlikely

Investigational Device: ThermoRF

Protocol No.: Thermo_0005

Version Date: Final 10-May-2016

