6. INVESTIGATIONAL PLAN

6.1. Overall Study Design and Plan

This is an open-label, single-center, single-treatment prospective evaluation of the ThermiRF device in the treatment of submental skin laxity. The purpose of this prospective study is to determine the effectiveness and safety of the ThermiRF device in achieving overall submental lift.

In this study, “Lift” is defined as a ≥ 20 mm² lift of the submental area after the ThermiRF treatment.

A total of 70 male and female healthy volunteers between the age of 35 and 65 will be considered for this study. Subjects who sign the informed consent form and meet all entry criteria will be enrolled in this study and will be assigned a unique number/code to preserve confidentiality.

A total of six study visits are planned as described below:

- Visit 1: Screening visit – (Day 1)
- Visit 2: Single Treatment visit
- Visit 3: Day 30 safety assessment (± 7 to 14 days)
- Visit 4: Day 60 safety and Image capture for validation exercise (± 7 to 14 days)
- Visit 5: Day 90 safety and effectiveness follow-up visit (± 7 to 14 days)
- Visit 6: Day 180 safety and effectiveness follow-up visit - (± 7 to 14 days)

Photo images (2D and 3D) will be collected at Visits 1, Visit 4 (on first 30 subjects only), and at Visits 5 and 6 using a standard camera (2D) and the Vectra XT system (3D). The purpose of the photos are to quantitatively and qualitative evaluate treatment effectiveness using objective and subjective assessments to measure physical changes to the skin’s microstructure and aesthetic skin features over time.

A skin elasticity assessment using the Cutomer® will be collected at Visits 1 (screening), 5 (Day 90) and 6 (Day 180) to assess if any biomechanical changes of the skin occurred as a result of the ThermiRF treatment.

Safety assessments will be collected using the Numerical Rating Scale (NRS) a 10-point scale, and adverse events reports (observed or reported).

The overall study duration is approximately 12 months (i.e., 5-6 month recruitment period and 6 month study visits).

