7. TREATMENTS

7.1. Treatment Administration

The single ThermoRF treatment to the neck (right/left) will be administered by the investigator in accordance with the protocol requirements, and with adherence to Good Clinical Practices (GCP) and standard of practice for surgical procedures.

Only study subjects who signed the informed consent and meet all entry criteria, will be enrolled and treated.

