### *10.2.4 PHYSICIAN – GLOBAL SATISFACTION QUESTIONNAIRE (P-GSQ)*

Physician will fill out the P-GSQ at Days 60, 90 and 180. Tables will summarize this in both the ITT and PP populations at each visit. The summary will include the number and percentage of subjects in each of the categories and the two-sided Clopper-Pearson 95% CI of the percentages. A binomial test of proportions will be carried out to compare those assessed with improvement versus no improvement. Additionally, a binomial test of proportions will test satisfaction, by testing those grouped as “Satisfied” or “Very Satisfied” verse all others. Further, likelihood of recommendation will be tested amongst those responding “Likely” or “Very Likely” verse all others.

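### P-GSQ item 4 asks for the physician's general intention to recommend the treatment, but SAP 10.2.4 plans a confidence interval and binomial test that count every subject's form as an independent answer

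*Protocol*

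**What the plan says.** - **The question.** Protocol Appendix 4, item 4: "How likely are you to recommend the treatment to your patients". Item 2 of the same form is tied to the case: "treatment how does the subject's skin" feels. Item 1 refers to the photographs, the current visit and the treated area.
- **Who answers, and when.** SAP 10.2.4: "Physician will fill out the P-GSQ at Days 60, 90 and 180". Protocol 6.1: "This is an open-label, single-center, single-treatment prospective evaluation of the ThermiRF device". Protocol 7.1 says the treatment "will be administered by the investigator in accordance with the protocol requirements", and Protocol 4.2 names the investigator, in the singular, as an evaluator of the secondary endpoints. Neither document says how many physicians complete the P-GSQ.
- **The analysis.** SAP 10.2.4: "The summary will include the number and percentage of subjects in each of the categories", with two-sided Clopper-Pearson 95% intervals, at each visit and in both the ITT and PP populations. For item 4, "Further, likelihood of recommendation will be tested amongst those responding" Likely or Very Likely against all others. No null proportion is given, and clustering by rater is not mentioned.
- **The shells.** P-GSQ Tables 7.2.3 and 9.2.3 and their listings stop at the satisfaction item and have no rows or column for recommendation. Footnote [4] of both tables still names the Likely and Very Likely categories.

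**The concern.** The exact binomial interval and test assume that each form is a separate, independent trial. That is defensible for an answer about the individual subject, and for S-GSQ item 4, which each subject answers personally. It is hard to defend for a question about the physician's patients in general, asked again on every form. An opinion that does not change from form to form adds no information when it is recorded again.

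At stake is false precision in a secondary effectiveness result. A reader of the report would see a recommendation rate with a tight interval and a very small p-value, and could take it as evidence from some 60 to 70 subjects when it may rest on one or a few opinions. SAP 2 and 3.1.2 foresee an interim report to support a manuscript or presentation, so such a figure could circulate outside the study report. With three visits and two populations, the SAP text calls for up to 3 × 2 = 6 such p-values.

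**Working it through.** The documents give no power or precision for item 4, so there is no planned figure to reproduce for it. As a check on the binomial method, the primary power in SAP 5 does reproduce: with null 0.45, true rate 0.70 × 0.875 = 0.6125, n = 70 and one-sided exact α = 0.05, at least 39 responders are needed, and power is 0.858 (the SAP states about 85%).

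**Inputs from the documents.** 70 enrolled; dropout 12.5%, so 70 × 0.875 ≈ 61 at Day 90 (Protocol 11.2); Day 60 limited to the first 30 subjects (Protocol 8.4); p-values below 0.001 printed as <0.001 (SAP 13.1).

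**Assumptions.** One responding physician; null 0.50 for item 4, with 0.45 as an alternative; within-physician correlation ρ from 0.1 to 1.

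**Step 1. Planned output if every form carries the same favourable answer.** The Clopper-Pearson lower limit for n out of n is 0.025^(1/n). The one-sided exact p-value is p0^n.

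| Forms n | 95% CI | p, null 0.50 | p, null 0.45 |
|---|---|---|---|
| 70 | 94.9% to 100% | 8.5 × 10⁻²² | 5.3 × 10⁻²⁵ |
| 61 | 94.1% to 100% | 4.3 × 10⁻¹⁹ | 7.0 × 10⁻²² |
| 30 | 88.4% to 100% | 9.3 × 10⁻¹⁰ | 3.9 × 10⁻¹¹ |

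All print as <0.001. Ten identical forms are enough against a null of 0.50: 0.5^10 = 0.00098.

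**Step 2. The same opinion counted once.** With n = 1 the interval is 2.5% to 100% and the one-sided p-value equals the null (0.50 or 0.45). No informative inference is possible.

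**Step 3. Partial dependence.** Effective sample size is n / (1 + (n − 1)ρ).

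- n = 61: ρ = 0.2, 0.5, 0.9 give 61/13 = 4.7, 61/31 = 2.0, 61/55 = 1.1.
- n = 70: ρ = 0.1, 0.5, 0.9 give 70/7.9 = 8.9, 70/35.5 = 2.0, 70/63.1 = 1.1.

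For the type I error, the count of favourable forms is taken as beta-binomial with mean 0.50 and both shape parameters 0.5(1 − ρ)/ρ. At n = 70 the one-sided exact test at 0.05 rejects from 43 favourable forms.

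| ρ | True one-sided type I error, n = 70 |
|---|---|
| 0.1 | 0.28 |
| 0.5 | 0.43 |
| 0.9 | 0.49 |
| 1 | 0.50 |

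The nominal level is 0.05. At Day 60, with 30 forms and ρ = 0.1, the error is 0.22.

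**The case against.** **The shells would not print this result.** This is true as they stand. The sentence in SAP 10.2.4 may be copied text: the same satisfaction and recommendation wording appears under S-GAIS (SAP 10.2.3), a scale with no such items. The SAP was also prepared from CRFs dated August 2016, later than the protocol form and not available here. But the SAP text and footnote [4] both still call for the test. The natural repair, adding the missing row, would put the unsupported interval and p-value into the report.

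**The line between items is a matter of reading.** Item 3, on satisfaction with the results, names no subject either, and a physician might answer item 4 with the subject at hand in mind. This stands in part: nothing shows that the answers will be constant, and ρ may be well below 1. Still, the results in item 3 can naturally be read as those of the subject whose form it is, while item 4 points explicitly to other patients. A shared rater alone is not the objection, so a reader should not extend the point to items 1 and 3 or to P-GAIS.

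**The size rests on unstated quantities.** The number of physicians, ρ and the null are all assumed. With one rater, ρ for a population of physicians cannot be estimated from the data. If the target were the share of subjects for whom this rater answers favourably, the design effect would not apply. The item's wording does not ask for that quantity, and the SAP does not define it. Two or three raters would still supply few independent opinions.

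**It is minor.** SAP 7.5 says secondary endpoints are not formally tested in support of labeling. That limits the consequence but does not make the planned interval valid.

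**Conclusion.** The point holds with limited reach. If one or a few physicians complete the P-GSQ, the forms are not independent for item 4, and the planned CI and p-value overstate the information. Under the stated assumptions, identical favourable answers on about 61 forms would print as 100% (94.1% to 100%), p<0.001, and the one-sided type I error at 70 forms runs from about 0.28 (ρ = 0.1) to 0.50 (ρ = 1).

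A reader might infer more than the documents support:

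- *The test rejects almost whatever the data.* It does not. The one-sided error is far above 0.05 but no more than 0.50 at a null of 0.50, and mixed answers near the null would not reject. Near-certain rejection needs a two-sided test, which is the default in Protocol 11, together with almost identical answers; even then the rejection may go in the unfavourable direction.
- *Up to 70 forms at every visit.* At Day 60 there are at most 30, and the documents disagree on whether the P-GSQ is collected then: Protocol 8.4 and SAP 10.2.4 include it, while Appendix 1 does not and the form offers only Days 90 and 180.
- *A single physician rates everyone.* This is an inference from the single center and the singular investigator, not a stated fact.

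The effect is confined to one sub-item of one of five secondary assessments. The primary endpoint, sample size and safety analyses are untouched.

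**What to change.** In SAP 10.2.4, for P-GSQ item 4 in both ITT and PP:

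1. Delete the binomial test of Likely or Very Likely against all others, and the Clopper-Pearson CI.
2. Report the item descriptively, as a count of forms in each answer category at each visit, with the number of responding physicians beside it.
3. Remove the Likely and Very Likely wording from footnote [4] of Tables 7.2.3 and 9.2.3 only. The S-GSQ tables keep theirs, because each subject answers that item.

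This also removes the conflict between the SAP text and the P-GSQ shells over the test. The count needs one line in those tables, without an interval or p-value. If the August 2016 CRF no longer carries item 4, the sentence in SAP 10.2.4 can simply go. Rewording the questionnaire is not advised: it would alter a form that may already be in use and would leave the same rater answering.

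The cost is a few lines of SAP text, one footnote, and the loss of one secondary p-value per visit and population that could not have been interpreted.

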APPENDIX 5 SUBJECT- GLOBAL SATISFACTION QUESTIONNAIRE (S-GSQ) OF THE NECK

STUDY NO.: THERMI_005	VISIT DAE:
SUBJECT ID:	VISIT DAY:  90  180
SUBJECT GLOBAL SATISFACTION QUESTIONNAIRE (S-GSQ) OF THE NECK	
Instruction:	

• Provide a copy of the before and after photo to the study participant PRIOR to administering the G• Direct the subject to the photo and review the lower part of the face using the “jawline”, “upper neck – under the chin” and “lower neck”• Have the subject provide responses to the following questions.	
1. Have you noticed any change with respect to “improvement” of the skin appearance of your neck?	 Yes, if “yes” please check all that apply:  Less sagging on the jawline and cheeks  Tighter/lift under the chin area  Smoother skin texture  Jaw line more defined  less wrinkles/lines  Other (specify); _____  No
2. Compared to “BEFORE” treatment how does your skin feel today (check all that apply)?	 Tighter  Firmer  Smoother  Make-up application easier  Shaving easier  No change from prior to treatment
3. How satisfied are you with the results of your treatment.	 Very Satisfied  Satisfied  Neutral  Dissatisfied  Very dissatisfied
4. How likely are you to recommend this treatment to family and friends?	 Very likely  Likely  Neutral  Unlikely  Vert unlikely

APPENDIX 6 CUTOMETER BROCHURE

CUTOMETER® DUAL MPA580 - MECHANICAL PARAMETERS OF THE SKIN

What does it measure?

The Cutometer® MPA 580 is a worldwide acknowledged standard device to measure elasticity and other biomechanical parameters of the skin. The Multiprobe Adaptor function allows to connect further probes additionally to the two Cutometer® probes.

The Measuring Principle

The measurement is based on suction. Negative pressure is created in the device and the skin is drawn into the aperture of the probe. Inside the probe the penetration depth is determined by a non-contact optical measuring system consisting of a light source and a light receptor, as well as two prisms facing each other, which project the light from transmitter to receptor. The light intensity varies due to the penetration depth of the skin. The resistance of the skin to be sucked up by negative pressure (firmness) and its ability to return into its original position (elasticity) are displayed as curves.

[figure not shown]
Fields of Application

[figure not shown]
The measurement with the Cutometer® is used as standard in dermatology and cosmetology

- It is indispensable for formulation, efficacy testing and claim support for all kinds of cosmetic products (especially anti-ageing products, firmness enhancing products).
- It is used for research and clinical diagnosis, e.g. measurement on scars. Also special applications like in gynaecology are possible.
- Other materials like food can also be assessed.

Advantages

- The modern, high quality electronics of the probe allow a very quick measurement.
- Several probe aperture sizes for different skin types and study requirements available.
- Two probes with different aperture sizes can be connected at the same time.
- A spring in the measuring head provides constant pressure on the skin.
- The low weight of the probe ensures easy handling. A multitude of elasticity related parameters can be calculated from the curves.
- The settings in the programme are very flexible and can be selected by the user according to different applications.
- All data of the curves can be transferred to spreadsheets (Microsoft Excel®) for further individual evaluation (up to four curves per sheet).
- Available solely as C+K MPA -System.

Technical Data

Dimensions: 39 x 22.5 x 7.6 cm, Probe: 10.7 cm x Ø 2.4 cm, Aperture: Ø 2 mm standard, (4, 6 or 8 mm on request), Weight: Device: 3.9 kg, Probe: 165 g incl. air tube, Power supply: ext. 100-240 VAC, 47-63 Hz, DC 12V/9A

Ua: µm penetration depth into the probe opening, expressed as curves

Technical changes may be made without prior notice.

Courage+Khazaka electronic GmbH since 1986
[name]
[contact] · [contact]
[contact] · www.courage-khazaka.de

CK
electronic

CUTOMETER® DUAL MPA580 - MECHANICAL PARAMETERS OF THE SKIN

Software & Parameters

The software of the Cutometer® dual MPA 580 allows to calculate a lot of interesting parameters. Here a short overview:

R-Parameters

- R0: This parameter represents the passive behaviour of the skin to force.
- R1: The ability of the skin to return to its original state.
- R2: Gross elasticity, the closer the value is to 1 (100 %) the more elastic the curve, very important parameter.
- R3: Last curve, compared to the maximum amplitude of the first curve. „Tiring effects“ of the skin are visible, as the amplitude increases with each new suction.
- R4: Last minimum amplitude compared to the first curve, „tiring effects“ of the skin are visible, as the ability of redefinition decreases with each new suction.
- R5: Net elasticity, the closer the value is to 1 (100 %) the more elastic the skin.

F-Parameters

These area parameters can only be taken in mode 1 and some will need 10 repetitions.

- F1: This area is deducted from the total area. A completely elastic material will show no area
- F2: Portion of the visco-elasticity on the elastic part of the curve. The smaller the value the higher the elasticity.
- F3: Portion of the elasticity compared to the complete curve, the closer the value is to 1 (100 %) the more elastic the skin.
- F4: The closer Ua of the first curve is to 0 the greater the ability of the skin to return into its original state.
- R9: Represents tiring effects of the skin after repeated sucking in of the skin. The smaller R9 the smaller the tiring effects.

[figure not shown]
[figure not shown]
[figure not shown]
Q-Parameters

A set of parameters developed by the scientist [name] has recently been added, showing interesting correlations between skin age and the elastic and viscoelastic recovery of the curves.

- Q0: Maximum recovery area, will go down with more firmness of the skin.
- Q1: Elastic recovery, will be higher with more firmness of the skin.
- Q2: Viscous recovery
- Q3: Viscoelastic recovery (overall elasticity) will be higher with more firmness of the skin.

at all, the closer the value to 0 the more elastic the material.

- F2: Area above the upper envelope-curve.
- F3: Area within the envelope curves.
- F4: The smaller F4 the more the skin resists to the suction (skin firmness).

Probe	Ua (µm)	Z (cm)	Q1 (µm)	Q2 (µm)	Q3 (µm)	Q4 (µm)	Q5 (µm)	Q6 (µm)	Q7 (µm)	Q8 (µm)	Q9 (µm)	Q10 (µm)
00	12.143	18.965	12.298	17.798								
01	8.026	8.604	8.398	8.996								
02	8.406	8.938	8.578	9.298								
03	8.205	8.726	8.478	9.138								
04	8.285	8.295	8.218	8.128								
05	8.940	9.697	9.244	9.947								
06	8.774	9.648	9.048	9.547								
07	8.256	8.735	8.562	8.987								
08	8.774	9.648	9.048	9.547								
09	8.000	8.110	8.048	8.062								
10	12.143	18.965	12.298	17.798								
11	8.026	8.604	8.398	8.996								
12	8.205	8.726	8.478	9.138								
13	8.406	8.938	8.578	9.298								
14	8.774	9.648	9.048	9.547								
15	8.774	9.648	9.048	9.547								
16	8.774	9.648	9.048	9.547								
17	8.774	9.648	9.048	9.547								
18	8.774	9.648	9.048	9.547								
19	8.774	9.648	9.048	9.547								
20	8.774	9.648	9.048	9.547								

Technical Data

Computer: Windows® XP, Vista or 7, 32 bit (not 64 bit!), performance must meet system requirements, USB 2.0

Technical changes may be made without prior notice.

Qu, Senior Research Scientist, R&D Skin Care, Amway Corporation, Ada, Michigan, USA

Courage+Khazaka electronic GmbH since 1986
[name]
[contact] · [contact]
[contact] · www.courage-khazaka.de

[figure not shown]
CK
electronic

Investigational Device: ThermiRF

Protocol No.: Thermi_0005

Version Date: Final 10-May-2016

